Incidence of treatment emergent adverse events (TEAEs) will be tabulated by primary system organ class (SOC) and by specific event within each primary SOC. TEAEs will be analyzed after treatment start on Day 1 through the end of the study.

Sample Size Calculation: A total sample size of 250 randomized participants per treatment group will provide at least 96% power to detect the treatment difference between each of the 2 atogepant doses (assumed equally effective) and placebo for the primary efficacy endpoint. This sample size was selected to provide sufficient power for the first 3 secondary endpoints. The power calculations are based on the following assumptions:

- 1) the treatment difference from placebo will be similar to the average value across the CM prevention studies for Botox® (Aurora 2010, Diener 2010) and TEV-48125 (Bigal 2015, Silberstein 2017). In particular, the assumed treatment difference from placebo in change from baseline in mean monthly migraine days across the 12-week treatment period is -2 days, and the standard deviation is 5.5 days.
- 2) the study statistical testing plan controls the overall type I error at 5%. The power calculations of the primary and secondary endpoints have taken the multiple comparisons into consideration by testing each dose versus placebo at a 0.025 significance level, 2-sided. Once the primary endpoint for each dose is significant at 0.025, 2-sided, the secondary endpoints will be tested sequentially.

Figure 1 Study Diagram

BID = twice daily; V = visit.

Table 1 **Schedule of Visits and Procedures**

Study Period	Screening/ Baseline (4 weeks)	Double-blind Treatment Period (12 weeks)						Follow-up Period (4 weeks)
		Visit # ^a	Visit 1	Visit 2 (Randomization)	Visit 3	Visit 4	Visit 5	
Day/Week	Week -4	Day 1	Week 2 (Day 14)	Week 4 (Day 28)	Week 6 (Day 42)	Week 8 (Day 56)	Week 12 (Day 84)	Week 16 (Day 112)
Visit Windows	Day -35 to Day -28	NA	± 3 days	± 3 days	± 3 days	± 3 days	+ 3 days	± 3 days
Obtain Informed Consent and participant privacy	X							
Obtain Informed Consent for future biomedical research (optional)	X							
Obtain Informed Consent for PK (optional)	X							
Obtain VCT consent and perform verification (United States and Canada only)	X							
Access IWRS	X	X	X	X	X	X	X	X
Assess inclusion/exclusion criteria	X	X						
Collect demographic information	X							
Collect medical history	X							
Collect migraine history	X							

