- ^f Clinical laboratory determinations include chemistry, hematology, INR, and urinalysis to be collected for all visits. Samples for serology and the urine drug screen will be collected only at screening (Visit 1).
- ^g PK sample should be collected prior to the first dose at Visit 2. One sample should be collected prior to the morning dose during one of the Visits 3 to 7, and the remaining samples should be collected 1 to 10 hours postdose.
- ^h Participant should begin using the eDiary as soon as it is dispensed. If it is subsequently determined that the participant has failed entry criteria, the eDiary should be returned to the site.
- ⁱ Participants must bring the eDiary to visits and review with coordinators.
- ^j Clinicians will complete on eTablet. The screening/baseline assessment of the C-SSRS will be completed. At all other visits, the ‘Since Last Visit’ C-SSRS will be completed.
- ^k Participant will complete on eTablet.
- ^l PRO measures should be administered prior to any tests and/or evaluations unless indicated otherwise in the protocol (eg, during Randomization Visit 2, some tests will be conducted prior to the PROs for eligibility).
- ^m EQ-5D-5L will be given on eDiary during 7 days in the baseline period and during specific time periods for Visit 1 to 7, except at Visit 8 (Week 16) where it will be administered on an eTablet.
- ⁿ eDiary will be collected on Visit 2 for screen failures.
- ^o Collected at Visit 7/ET only for participants who complete the double-blind treatment period.
- ^p Collected at Visit 8/Follow-up only for participants who discontinue from the double-blind treatment period.
- ^q The first dose of study intervention should be taken at the study site.

1. Background and Clinical Rationale

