6.1 Efficacy Measures

Efficacy assessments will be based on information recorded by the participant. An eDiary will be used daily at home to collect data on headache frequency, duration, characteristics, and symptoms; acute medication use and triptan use, which will be collectively applied to define migraine days and headache days per the criteria listed in Sections 6.1.1, 6.1.2, and 6.1.3.

The AIM-D, Activity Level, and Activity Limitation will also be collected daily via an eDiary. EQ-5D-5L will also be collected via an eDiary for a period of 1 week in the screening period (administered on Study Day 22 through 28 for a total of 7 days after screening), randomization (Study Day 1) until Visit 3 (14 consecutive days from randomization), Visit 4 (± 3 days, ie, Study Days 25 to 31 from randomization for a total of 7 days), Visit 5 (± 3 days, ie, Study Days 39 to 45 from randomization for a total of 7 days), Visit 6 (± 3 days, ie, Study Days 53 to 59 from randomization for a total of 7 days), and Visit 7 ($- 7$ days, ie, Study Days 77 to 83 from randomization for a total of 7 days). At Visit 8, the EQ-5D-5L will be administered on an eTablet. Additional health outcome measures, namely, the PSSM scale, HIT-6, MIDAS, PGIC, WPAI:MIGRAINE, PGI-S, MSQ v2.1, PROMIS-PI, and PHQ-9 will also be administered on an eTablet at specified clinic visits.

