7.2 Collection and Derivation of Primary and Secondary Efficacy Assessments

On a daily basis during the 28-day baseline period and throughout the study, participants are to record, into an eDiary, information on the daily total duration of headache, headache specific characteristics and symptoms, the worst pain severity, and use of any acute medication. Participants will be able to report headache data, including absence of headache, for the day of the diary report and for the day immediately prior to the day of the diary report, as long as information reported is for a time subsequent to the participant's most recent report. This is defined as a 1-day "missing-recall" window.

Following randomization on Day 1, there are 4 visits at 2-week intervals, followed by 2 visits at 4-week intervals; altogether encompassing a 12-week double-blind treatment phase of the study and a 4-week follow-up phase. In practice, there may or may not be exact 2-week or 4-week durations between 2 consecutive visits, and the visits might not align with each 28-day period recorded in the eDiary (ie, Weeks 1 to 4, 5 to 8, and 9 to 12, corresponding to Days 1 to 28, 29 to 56, and 57 to 84). Therefore, for data analysis purposes, the number of migraine days during the last 28 days prior to the randomization date, will serve as the baseline, and change from baseline will be calculated for consecutive 28-day periods beginning with the date of the first dose of study intervention.

In order to be randomized, a participant should be in the baseline phase for at least 28 days and must report diary data for at least 20 days (including missing recall) during the 28-day baseline period. If less than 28 days of baseline data are reported, the number of headache days and other such counting variables for baseline will be prorated to standardize the count to a 28-day equivalent. Subsequent to treatment start, the number of headache days will be counted in successive and non-overlapping 4-week (ie, 28-day) windows. Headaches that continue into a subsequent 4-week period will be counted (with recorded severity and duration) as occurring in each period.

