8.4.1 Visit 1 (Screening/Baseline) Day -35 to Day -28

- Obtain informed consent and participant privacy.
- Obtain informed consent for future biomedical research (optional).
- Obtain informed consent for PK substudy (optional).
- Obtain VCT consent and perform verification at participating sites (United States and Canada only).
- Register participant in IWRS.
- Assess inclusion/exclusion criteria.
- Collect demographic information.

- Collect medical history.
- Collect migraine history (3-month retrospective) and confirm diagnosis.
- Review prior medications taken in the past 6 months, and all prior headache medications including migraine prophylactic medication use and concomitant medications/procedures.
- Assess C-SSRS on eTablet (the ‘Screening/Baseline’ assessment of the C-SSRS will be completed).
- Collect ASC-12 on eTablet.
- Perform physical examination.
- Collect vital sign measurements including: height, weight, sitting and standing pulse rate, respiratory rate, sitting and standing BP, and body temperature.
- Collect start date (first day) of last menstrual cycle for women having menstrual cycles.
- Perform and transmit ECG.
- Perform urine pregnancy test (for women of childbearing potential only).
- Collect urine for drug screen.
- Collect clinical laboratory determinations including: chemistry, hematology, INR, screening serology, and urinalysis.
- Collect blood for future biomedical research (for those participants who consented)
- Provide eDiary, along with training and instructions. Participants to bring eDiary to all visits.
- Review and assess AEs.

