	4 Days after Initial Dose	Treatment Day 5
	5 Days after Initial Dose	Treatment Day 6
	6 Days after Initial Dose	Treatment Day 7

The analysis visit windows for MSQ v2.1 and HIT-6 for mITT Population and Off-treatment Hypothetical Estimand Population are defined as follows:

Table 16.1-5. Efficacy Analysis Visit Definitions for MSQ v2.1 and HIT-6

Analysis Phase	Analysis Visit (Derived)	Scheduled Study Visit (eCRF)	Window
Pretreatment	Baseline	Visit 2 (Randomization)	Treatment Day ≤ 1
Double-Blind Treatment Period	Week 4	Visit 4	Treatment Day [2, 41]
	Week 8	Visit 6	Treatment Day [42, 69]
	Week 12	Visit 7/ET	Treatment Day [70, end of the double-blind treatment period]
Follow-up	Week 16 (Follow-up)	Visit 8	Treatment Day [end of the double-blind treatment period +1, min(end of last study visit, 115)]

ET = early termination. Follow-up visit will not be included in the MMRM analysis and will only be used in summary statistics.

Table 16.1-6. Efficacy Analysis Visit Definitions in the Off-Treatment Hypothetical Estimand Approach for MSQ v2.1 and HIT-6

Analysis Phase	Analysis Visit (Derived)	Window
Pretreatment	Baseline	Treatment Day ≤ 1
On or after the first dose of study intervention	Week 4	Treatment Day [2, 41]
	Week 8	Treatment Day [42, 69]
	Week 12	Treatment Day [70, 97]
	Week 16	Treatment Day [98, end of last study visit]]

ET = early termination. Follow-up visit will not be included in the MMRM analysis and will only be used in summary statistics.

The analysis visit windows for EQ-5D-5L for mITT Population and Off-treatment Hypothetical Estimand Population are defined as follows:

Table 16.1-7. Efficacy Analysis Visit Definitions for EQ-5D-5L

Analysis Phase	Analysis Visit (Derived)	Scheduled Study Visit (eCRF)	Window
Pretreatment	Baseline	Visit 2 (Randomization)	Treatment Day [-7, -1]
Double-Blind Treatment Period	Week 1-2	Visit 3	Treatment Day [1, 14]
	Week 4	Visit 4	Treatment Day [25, 31]
	Week 6	Visit 5	Treatment Day [39, 45]
	Week 8	Visit 6	Treatment Day [53, 59]
	Week 12	Visit 7/ET	Treatment Day [77, minimum(end of the double-blind treatment period, 83)]
Follow-up	Week 16 (Follow-up)	Visit 8	Treatment Day [end of the double-blind treatment period +1, min(end of last study visit, 115)]

ET = early termination. Follow-up visit will not be included in the MMRM analysis and will only be used in summary statistics.

Table 16.1-8. Efficacy Analysis Visit Definitions in the Off-Treatment Hypothetical Estimand Approach for EQ-5D-5L

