The descriptive system comprises 5 dimensions (mobility, self-care, usual activities, pain/discomfort, anxiety/depression). The mobility dimension queries the participant’s walking ability. The self-care dimension queries the participant’s ability to wash or dress by himself. The usual activities dimension assesses the participant’s performance in “work, study, housework, family or leisure activities”. The pain/discomfort dimension measures how much pain or discomfort a participant has. The anxiety/depression dimension assesses how anxious or depressed a participant is. The respondent is asked to indicate his/her health state by ticking (or placing a cross) in the box against the most appropriate statement in each of the 5 dimensions. The scoring range of the EQ-5D descriptive system is typically from 0 (dead) to 1 (full health). The second component of the EQ-5D-5L is a visual analogue scale (EQ-VAS) by which participants can rate their overall health from 0 (worst imaginable health state) to 100 (best imaginable health state).

With the EQ-5D-5L, rating levels can be coded as numbers 1, 2, 3, 4 or 5 which correspond to having no problems, having slight problems, having moderate problems, having severe problems, and being unable to do/having extreme problem. As a result, a participant's health state can be defined by a 5-digit number by combining the numeric levels from the 5 dimensions, ranging from 11111 (having no problems in all 5 dimensions) to 55555 (having extreme problem in all 5 dimensions). The US-based value set for the EQ-5D-5L will be derived using an international standardized protocol ([Pickard et al., 2019](#)).

EQ-5D-5L will be captured on eDiary during 7 days in the screening/baseline period and during specific time periods for Visit 1 to 7, except at Visit 8 (Week 16) where it will be administered on an eTablet. The index score and VAS score for a specific period will be calculated as the average of available scores in that period respectively if at least 50% of daily scores are available; otherwise, the scores will be set as missing. For example, for a period of 14 days, at least 7 assessments are required; and for a period of 7 days, at least 4 assessments are required.

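### Protocol 6.1 does not say how the baseline EQ-5D-5L days are counted; if they run from Visit 1, the SAP's seven-day baseline window discards compliant data for early Visit 1 dates

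*SAP*

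**What the plan says.** Protocol 6.1 has the baseline EQ-5D-5L completed on the eDiary, "administered on Study Day 22 through 28 for a total of 7 days after screening". Protocol 8.4.1 allows a range for the screening visit: "Visit 1 (Screening/Baseline) Day -35 to Day -28", which is eight permitted days. Protocol 7.2 requires that "a participant should be in the baseline phase for at least 28 days", so the phase may last longer than 28 days.

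The SAP counts from the other end. SAP 16.1 sets Day 1 as the date of first double-blind dose, which Protocol 5.6 places at Visit 2. The baseline row of Table 16.1-7 (mITT) and Table 16.1-8 (off-treatment hypothetical estimand) is "Treatment Day [-7, -1", that is, Days -7 to -1 inclusive. SAP 16.2.2 averages the available daily scores if at least half are present and otherwise sets the period to missing: "for a period of 7 days, at least 4 assessments are required", and "for a period of 14 days, at least 7 assessments are required". SAP Table 10.2-3 assigns the EQ-5D-5L index to the change-from-baseline MMRM. Table 10.2-2 says that model uses baseline as a covariate and observed cases without imputation.

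**The concern.** Collection is described relative to screening, and the analysis window relative to first dose. The two coincide only if the interval between them is fixed, and the permitted Visit 1 range lets it vary by a week. Neither document says how the baseline days 22 to 28 are counted.

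If they run from Visit 1, an early screening visit moves the whole collection week back while the SAP window stays put. A participant who completed every scheduled questionnaire could then have no EQ-5D baseline and drop out of the EQ-5D change-from-baseline analysis in both populations, although the data exist. The same would hold for the VAS if it is analysed: Table 10.2-3 lists a VAS model, while SAP 10.1.2 and 16.2.2 say only the descriptive system is summarized.

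EQ-5D-5L is more exposed than the other instruments. MSQ, HIT-6, PGI-S, WPAI, PROMIS-PI, MIDAS and PHQ-9 use an open-ended baseline window (any day up to Day 1), and the headache diary is kept daily. EQ-5D-5L pairs seven days of collection with a closed seven-day window.

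**Working it through.** **The plan's own figure.** Half of 7 is 3.5, rounded up to 4. Half of 14 is 7. Both match SAP 16.2.2.

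**Inputs.** Collection on days 22 to 28 (Protocol 6.1); Visit 1 on Day -v with v = 28 to 35 (Protocol 8.4.1 and Table 1); window Days -7 to -1 (SAP Tables 16.1-7 and 16.1-8); minimum 4 (SAP 16.2.2). Every scheduled entry is taken as completed, and first dose is on the Visit 2 day.

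**Reading A: forward from Visit 1, with Visit 1 as day 1.** Day k falls on -v + (k - 1), so collection runs from -v + 21 to -v + 27. For v = 28 this is Days -7 to -1; for v = 35 it is Days -14 to -8. Scores in the window = 35 - v.

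**Reading B: forward from Visit 1, with the next day as day 1.** Day k falls on -v + k, so collection runs from -v + 22 to -v + 28. For v = 28 the last scheduled day lands on Day 1 (there is no Day 0), leaving 6 scores. For v = 29 all 7 fit. For v = 30 to 35 the count is 36 - v.

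**Reading C: days 22 to 28 of the 28 days ending just before randomization.** Day k falls on -29 + k, so day 22 is Day -7 and day 28 is Day -1. All 7 scores fit whatever the Visit 1 date.

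Scores inside Days -7 to -1:

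| Visit 1 on Day | -28 | -29 | -30 | -31 | -32 | -33 | -34 | -35 | Days below 4 |
|---|---|---|---|---|---|---|---|---|---|
| A | 7 | 6 | 5 | 4 | 3 | 2 | 1 | 0 | 4 of 8 |
| B | 6 | 7 | 6 | 5 | 4 | 3 | 2 | 1 | 3 of 8 |
| C | 7 | 7 | 7 | 7 | 7 | 7 | 7 | 7 | 0 of 8 |

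**A wider window, Days -14 to -1.** Reading A gives 7 on all eight days; B gives 6 on Day -28 and 7 on the other seven; C gives 7 throughout. With a minimum of 4, no permitted day fails under any reading.

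**Why the minimum must be fixed with the window.** A 14-day window could be read as invoking the minimum of 7. Only seven scores are scheduled, so one missed entry would void the baseline, and Visit 1 on Day -28 under B (6 scheduled scores) would fail by design. As an illustration only, assume each of 7 entries is completed independently with probability 0.9:
- minimum 7: P(missing) = 1 - 0.9^7 = 1 - 0.478 = 0.522
- minimum 4: P(3 or fewer of 7) = 0.003

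The 52% would be a side effect of an incomplete fix, not a feature of the present plan.

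**The case against.** The strongest reply is that the window is the sponsor's own translation of Protocol 6.1. The SAP's double-blind EQ-5D-5L windows (Days 1-14, 25-31, 39-45, 53-59 and 77-83) copy that section day for day, which suggests Days -7 to -1 were meant as days 22 to 28 of a 28-day baseline. Table 16.1-7 ties the baseline row to Visit 2. Protocol 7.2, SAP 16.1 and SAP 16.10 all anchor a baseline period to the 28 days before randomization. Protocol 6.1 also gives the label Study Day 1 to randomization in the same sentence, which sits badly with calling Visit 1 day 1. Under B with Visit 1 on Day -28, the last baseline entry would collide with the start of post-randomization collection. All of this stands as evidence for reading C.

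It does not settle the matter. The sentence dates the baseline week from screening, whereas the later windows are counted from randomization, and a baseline phase of more than 28 days is expressly possible. The instruction "Participant should begin using the eDiary as soon as it is dispensed" (Protocol Table 1, footnote h) adds little, because EQ-5D-5L is not given from the day of dispensing.

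A second reply is that a separate health-outcomes SAP (Protocol 7.2.3.1, SAP 16.2.2) may contain a fallback. That is fair: it is not among the documents, so a reader should not infer that the sponsor has no fallback anywhere. What can be said is that this SAP sets the window, the minimum and the model, states in section 18.0 that the health outcome endpoints were brought into it, and offers no fallback itself.

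**Conclusion.** The point holds as a conditional one. The documents leave the counting of the baseline EQ-5D-5L days open. On either forward count from Visit 1, a fully compliant participant screened on the earliest 4 (A) or 3 (B) of the 8 permitted days has fewer than 4 scores in the window and no EQ-5D baseline under this SAP. On the backward count there is no loss.

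A reader might infer that counting from Visit 1 is plainly intended, or that nearly half of participants would lose their baseline. Neither is supported. The text points both ways, and 3 or 4 of 8 are calendar days, not participants. The distribution of Visit 1 dates is not given, so the share affected could be anywhere from 0% to 100%. The counts also assume full diary completion and first dose on the Visit 2 day.

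The consequence is limited. Visit 1 timing is fixed before randomization, so the main cost is lost data and precision. EQ-5D-5L lies outside the testing hierarchy, and no primary, secondary or alpha-controlled conclusion changes. This is a desirable clarification, not a threat to the trial's main results.

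**What to change.** 1. In the baseline row of SAP Tables 16.1-7 and 16.1-8, define baseline as *the last 7 available daily EQ-5D-5L records on Treatment Days -14 to -1*.
2. Add to SAP 16.2.2: *Baseline is treated as a 7-day period needing at least 4 records; the 14-day minimum of 7 does not apply.*
3. State in Protocol 6.1 whether the baseline days are counted forward from Visit 1 (and, if so, whether Visit 1 itself is counted) or back from randomization. Do not use the label Study Day 1 for this, since that sentence already gives it to randomization.
4. Align the separate health-outcomes SAP.

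The cost is one row in two tables, one added sentence, one protocol clarification and a matching line in the other SAP. No new data are needed. If reading C was intended, the change does no harm, because all seven scheduled days also lie in the wider window. The window ends before Day 1, so it does not overlap the Week 1-2 window. The downside is that, on a forward count, some participants' baseline ends up to a week before first dose (Day -8 for Visit 1 on Day -35 under reading A).

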16.2 DERIVED EFFICACY AND HEALTH OUTCOME DATA

16.2.1 Derivation of Efficacy Endpoints Based on eDiary Data

For analysis purposes, four weeks (28 days) will be considered as one month. On a daily basis during the 4-week baseline period and throughout the study, participants are to record eDiary information on the duration of headache, headache specific characteristics and symptoms, the pain severity, and use of any acute headache pain medication. Daily headache diary data consists of data from “today’s diary” completed on that day and “yesterday’s diary” completed on the following day. Participants are to report headache data in “today’s diary” in the evening 19:00 to 23:59 and to complete “yesterday’s diary” on the following day to add the remaining headache data of previous evening until midnight. In case participants miss “today’s diary”, they can report the whole-day headache data in “yesterday’s diary” on the following day. In case participants miss “yesterday’s diary”, headache data from “today’s diary” alone will be used as daily headache diary data. If both “today’s diary” and “yesterday’s diary” are missing on one day, the daily headache diary data will be treated as missing.

Daily headache diary data will be merged from “today’s diary” and “yesterday’s diary” as following and will be used to derive migraine day and headache day.

- Daily headache total duration: summation of headache durations from “today’s diary” and “yesterday’s diary”
- Daily headache pain severity: the worst pain severity from “today’s diary” and “yesterday’s diary”
- Daily headache characteristics and symptoms: present if present in one of “today’s diary” and “yesterday’s diary”
- Daily acute headache medication usage: combination of acute headache medications usage from “today’s diary” and “yesterday’s diary”

Moderate/severe headache day is defined as a headache day during which the maximum pain severity is either moderate or severe.

Severe headache day is defined as a headache day during which the maximum pain severity is severe.

If a participant confirmed no headache for the Question 1 in eDiary, then the participant will not answer subsequent questions related to headache symptoms, duration, and acute headache medication use by design. Thus, the acute medication use for that diary ('today' or 'yesterday') will be treated as 'No' when deriving acute medication use day.

If a participant reported multiple records on the same day for one specific category ('Today' or 'Yesterday') and records are inconsistent, then the records for that eDiary category on the date with discrepancy will be excluded from endpoint derivation and thus excluded from the analyses. The corresponding records will be flagged in the analysis datasets. If there are duplicated records of daily diary data for the same participant on the same day with the same type, the set of records with the last form access datetime will be used in the analysis because records are duplicated.

The monthly migraine days is defined as the total number of recorded migraine days in the eDiary divided by the total number of days with eDiary records during each monthly period and multiplied by 28. For baseline, a minimum of 20 days' eDiary data during the 4-week baseline period is required for the migraine days to be evaluable. A minimum of 14 days' eDiary data during a postbaseline monthly treatment period is required for the migraine days to be evaluable for that particular period. If a participant does not have at least 14 days of diary data for a monthly treatment period, the migraine days for that period will be considered as missing. Migraine days will be derived for each participant at baseline and for each postbaseline monthly treatment period (Weeks 1-4, 5-8, 9-12). The same method to derive monthly migraine days will be used to derive monthly headache days, monthly acute medication use days, monthly triptan use days, monthly cumulative headache hours, monthly headache day pain intensity, monthly moderate/severe headache days, and monthly severe headache days.

If a participant confirmed that acute medications were taken and entered medications in the eDiary, then the acute medication use day will be set to 'Yes'. If a subject reports 'Yes' to the intake of

allowed medication(s) to treat an acute migraine but does not list any of them in the diary, then the acute medication use days will not be counted in this situation and vice versa.

For weekly data analysis purposes, baseline is defined to be the baseline derived in monthly basis divided by 4, and change from baseline in the weekly migraine days will be calculated for consecutive 7-day periods beginning with Day 1. Subsequent to treatment start, the number of headache days will be counted in successive and non-overlapping 1-week (i.e., 7-day) windows. Headaches that continue into a subsequent 1-week period will be counted (with recorded severity and duration) as occurring in each period. If any postbaseline eDiary window for a participant has at least 4 but less than 7 days of reported data, the prorated approach will be used. If a participant reports less than 4 days of headache data, the participant's observed counts in that particular 7-day eDiary window will be set to missing for that window.

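### When a day's 'Today' diary records conflict, SAP 16.2.1 drops them but can still score the day from the late-evening 'Yesterday' entry, so a true migraine day may count as an observed non-migraine day

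*SAP*

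**What the plan says.** SAP 16.2.1 builds each diary day from two entries. 'Today' is completed "in the evening 19:00 to 23:59". Participants are then "to complete “yesterday’s diary” on the following day to add the remaining headache data of previous evening until midnight". 'Yesterday' can carry the whole day only if 'Today' was missed. Protocol 7.2 points the same way: back-reporting is allowed "as long as information reported is for a time subsequent to the participant's most recent report".

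The merge takes the sum of the two durations, the worse of the two severities, any symptom present in either entry, and the combined medication use. A missed 'Yesterday' is covered explicitly: 'Today' alone is used. On missingness the rule is: "If both “today’s diary” and “yesterday’s diary” are missing on one day, the daily headache diary data will be treated as missing".

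For inconsistent records of one type on one day, "the records for that eDiary category on the date with discrepancy will be excluded from endpoint derivation and thus excluded from the analyses". Affected records are to be flagged in the analysis datasets. A separate sentence, which keeps the latest form access, covers duplicated records and does not resolve inconsistent ones.

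Monthly migraine days are the recorded migraine days divided by the days with eDiary records, times 28. At least 20 diary days are needed at baseline and 14 in each later month. The same method gives monthly headache days and acute medication use days.

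**The concern.** The exclusion is made by diary type, whereas missingness is decided for the whole day. Nothing connects the two when 'Today' is excluded because of a conflict rather than missed. A participant who completed 'Today' has put most of the day there, so the surviving 'Yesterday' entry holds only what came later. The derivation nevertheless treats that fragment as a complete day.

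For such a day the merged status can only be kept or lowered, because one of the two sources feeding a sum, a maximum and an any-present rule has been removed. If the fragment reports no headache, acute medication use is also set to no.

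The affected counts feed the primary endpoint and the first three secondary endpoints: headache days, acute medication use days and the 50% responder rate. What is at stake is misclassified days, some of them days on which every conflicting record agrees that a migraine occurred.

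**Working it through.** **A figure from the plan, reproduced.** No stated figure is in dispute. As a check, the primary power (SAP 14.0: 250 per arm, difference 2 days, SD 5.5, two-sided 0.025) is Φ(2 / (5.5 × √(2/250)) − 2.241) = Φ(4.066 − 2.241) = 96.6%, against 96% stated.

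**How much of the day survives.** The 'Yesterday' add-on covers from the 'Today' entry until midnight: at most about 5 h after a 19:00 entry, 2 h after 22:00 and 1 h after 23:00. SAP 10.1.1 requires at least 2 h of headache for a migraine day unless a triptan or ergot was used. After a 'Today' entry later than 22:00, the fragment cannot meet that criterion unless it records such a drug.

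**An example day.** Two 'Today' records both give a 6-hour throbbing headache of moderate pain. One reports nausea and the other does not. The add-on reports no further headache.

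- Record with nausea: two characteristics, one symptom and at least 2 h, so criteria A, B and C are met.
- Record without nausea: two characteristics, no symptom and at least 2 h, so criteria D and E are met.
- Under SAP 16.2.1: both 'Today' records are excluded, 'Yesterday' remains, and the day is scored as no headache, no migraine and no acute medication. It still counts as a diary day.

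The second characteristic matters. With throbbing alone, the record without nausea would not qualify.

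**Monthly count.** Assume 28 diary days and 15 true migraine days, of which k have conflicting 'Today' records and a negative add-on.

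| k | As written: 28 × (15−k)/28 | Day missing: 28 × (15−k)/(28−k) |
|---|---|---|
| 1 | 14 | 14.52 |
| 2 | 13 | 14.00 |
| 3 | 12 | 13.44 |

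If all conflicting records qualify and that status is kept, the count stays at 15.

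Each lost migraine day lowers the monthly value by 28/(diary days). That is 1 day with 28 diary days and 2 days with 14: for example, 9/14 × 28 = 18 falls to 8/14 × 28 = 16.

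**Responder status.** Assume baseline 16 and 9 true migraine days in each month, so the participant is a non-responder (threshold 8). Losing one day per month gives 8.0 as written, a responder. With the day missing, the value is 28 × 8/27 = 8.30, a non-responder.

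**Baseline.** The same rule applies there. One baseline day lost from 16 gives 15, and the 50% threshold moves from 8 to 7.5, which makes response harder.

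**Scale in an arm.** The conflict rate is not given. Assume a share of participants have one affected migraine day in one of three months with 28 diary days. Each three-month mean then falls by 1/3 = 0.33 day, and the arm mean by 0.003 day at 1% or 0.03 day at 10%, against an assumed effect of 2 days. If instead a share f of the effect were lost (assumption), power would be 96.3% at f = 1%, 95.9% at 2% and 94.7% at 5%.

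**The case against.** **The SAP never says in one sentence that such a day is scored from 'Yesterday' alone.** True. It follows from combining the type-level exclusion, the both-missing rule and the merge rules. No other sentence prevents it. SAP 16.2.2 words its exclusion for the health-outcome diary endpoints by date, without the type limit, but does not extend that to the headache data.

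**Conflicts should be rare.** Protocol 7.2 limits a report to time after the last one, so two 'Today' records describing the same hours are an exception. Harm also needs an existing 'Yesterday' entry and a fragment that does not itself qualify. This stands as a limit on size. The SAP does anticipate conflicts, since it writes a rule for them.

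**A reader might infer that the rule can only lower monthly counts.** It cannot be put that way. If a non-migraine day has conflicting 'Today' records and no 'Yesterday' entry, it becomes missing and leaves the denominator: 28 × 15/27 = 15.56, which is above 15. The one-way effect holds only for days scored from the fragment.

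**A reader might also infer that the rule favours atogepant.** The documents do not support this. The rule is the same in all arms of a double-blind trial, and it affects baseline as well as follow-up. If post-baseline conflicts fell in proportion to migraine days, the arm with more migraine days would lose more of them and the difference would shrink.

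**Conflicts may be likelier on headache days.** A no-headache entry skips the later questions and leaves fewer fields to disagree. That is plausible reasoning, but no data in the documents show it.

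**Setting days to missing is not neutral either.** Agreed: 14.5 is still below 15. That is why the status should be kept where all records agree.

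**Conclusion.** The point holds on the text as written. A day whose 'Today' records conflict, and for which a 'Yesterday' entry exists, is judged on a late-evening remainder and counted as fully observed. Its status can stay the same or fall, so true migraine, headache or acute medication days can enter the primary and first three secondary endpoints as negatives.

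Per participant-month with 28 diary days, the loss is 1 day for each affected migraine day, or about 0.5 day relative to treating one such day as missing in the 15-day example. These figures assume that every conflict falls on a migraine day with a negative add-on. At arm level the size is unknown and would be small if conflicts are rare.

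This is misclassification at baseline and post-baseline in all arms. Neither a between-arm bias nor a fixed direction on change from baseline is shown, and nothing here suggests that the primary conclusion would change. It is worth correcting because it turns partly unknown days into observed ones and the remedy is cheap.

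**What to change.** Replace the conflict rule in SAP 16.2.1, for 'Today' records, with text such as:

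*If a participant has inconsistent 'Today' records for one date, each record will be merged with the 'Yesterday' record for that date, if present, and migraine-day, headache-day and acute-medication-day status will be derived from each merge. If all merges give the same status for an endpoint, that status will be used. Otherwise the day will be missing for that endpoint and will be removed from that endpoint's proration denominator.*

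Also report the number of flagged conflict days by arm and period (baseline and each 4-week period). The SAP already requires the flag, so the count is readily available and would settle the question of size. If the main derivation can no longer be changed, run this one as a sensitivity analysis.

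Cost: a short replacement text and minor programming. A few days become missing, denominators may differ slightly between endpoints, and a month close to the 14-day minimum could become non-evaluable.
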